12.3 Investigator Assessment of Adverse Events

If a diagnosis is clinically evident (or subsequently determined), the diagnosis rather than the individual signs and symptoms or lab abnormalities will be recorded as the AE.

All solicited (see Table 9 below) and unsolicited AEs will be recorded through 7 days after each vaccination, including injection site reactions, or until resolved. After that period, only unsolicited AEs (including symptomatic malaria), SAEs, UPs, and NOCIs will be recorded. Note that a positive BS without associated clinical symptoms (i.e., asymptomatic parasitemia) will not be reported as an AE. Clinical or symptomatic malaria will be reported as an AE.

Table 9. Solicited Adverse Events

Systemic adverse events
Fever (temperature ≥38.0 °C)
Headache
Nausea/Vomiting
Diarrhea
Abdominal pain
Fatigue
Malaise
Myalgia
Arthralgia
Urticaria
Local reactogenicity
Injection pain/tenderness
Injection erythema/redness
Injection swelling
Injection induration
Injection pruritus
Limitation of arm movement
Limitation of arm movement

Abbreviations: ALT, alanine transaminase; ANC, absolute neutrophil count; AGC, absolute granulocyte count; CR, creatinine; WBC, white blood cell.

Additional laboratory abnormalities other than those specified as safety labs in the protocol should be reported as AEs if they require intervention. Interventions include, but are not limited to, discontinuation of treatment, dose reduction/delay, additional assessments, or concomitant treatment. In addition, any medically important laboratory abnormality may be reported as an AE at the discretion of the investigator. This could include a laboratory result for which there is no intervention, but the abnormal value suggests a disease or organ toxicity. In addition, , all laboratory AEs will be collected and graded through 14 days after the first and second vaccination and 28 days after the third vaccination or until resolved.

The investigator will assess all AEs with respect to seriousness (criteria listed above), severity (intensity or grade), and causality (relationship to study agent and relationship to research) according to the following guidelines.

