14.2 Primary Objective

To assess safety and reactogenicity of administration of Pfs230D1-EPA/Matrix-M (all Arms):

- The frequency of systemic and local AEs will be summarized.
- A line listing of each clinical and laboratory AE classified as local, solicited, or other will be displayed in tables stratified by vaccine allocation.

- AEs will be summarized by severity and relationship to vaccine.
- The proportion of subjects with at least 1 AE will be compared by study group, and tests will be performed to assess whether these groups differ with respect to these proportions. To evaluate the difference in AEs between the initial vaccination and the subsequent vaccinations, a Wilcoxon signed-rank test (WSRT) will be performed, where the response for each subject is the difference between the numbers of AEs in the 7 days following each vaccination. To compare number and severity of AEs between control and vaccine arms, the Wilcoxon-Mann-Whitney test (WMW, also known as Wilcoxon rank sum test and Mann-Whitney U test) as well as linear regression may be used.
- SAEs occurring within the study period will be listed by relationship to vaccine.

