⁽¹⁾ Visit windows are based off timing of days post the preceding vaccination; (2) A complete physical exam will be performed at the screening visit. (3) Blood draw amounts are "up to" the mL listed for each laboratory. If less than that amount is collected, it will not be considered a deviation. (4) As per FDA guidelines, study days are listed with Day of Immunization #1 and Day 1 (rather than Day 0). Note that the study visits scheduled for Study Days 281, 337 and 393 may be conducted as phone calls if the participant is not able to come to the study site in person. * Hemoglobin typing will be done at the Day - 7 visit.

Day to Day Schedule

Study Day -7 (±7 days; Drug Treatment Visit)

- 1. Perform basic history and focused physical examination, emphasizing examination of any acute complaints.
- 1. Record vital signs (blood pressure, temperature, and heart rate).
- 2. Record AEs and concomitant medications, if applicable.
- 3. Obtain approximately 56 mL of blood for CBC with differential and platelet count, ALT, creatinine, malaria blood smear and PCR, hemoglobin typing, anti-Pfs230 antibody ELISA, standard membrane feeding assay (SMFA), cellular assays, transcriptional analysis.
 - If safety labs were obtained for screening within ≤ 2 days prior to day -7, can use for study day -7 visit and do not need to repeat.
- 4. For females, obtain a urine or serum sample for β-hCG testing. Ensure that the test is negative before proceeding.
- 5. For females, ensure agreement and compliance with pregnancy prevention before AL dosing.

Study Day 1 (±0 days; day of Vaccination #1)

The following evaluations/procedures will be completed before vaccination:

- 1. Ensure that all inclusion/exclusion criteria are met.
- 2. Ensure that CBC, ALT, creatinine, HIV, and urine results from screening are within protocol-defined limits (see Exclusion Criteria above) before vaccinating
- 3. Perform basic history and focused physical examination, emphasizing examination of any acute complaints.
- 4. Record vital signs (blood pressure, temperature, and heart rate).
- 5. During the physical examination, study staff will educate the subject regarding signs and symptoms of potential adverse events (AEs) and indications for use of antipyretics if fever, headache, or malaise occurs.
- 6. For females, obtain a urine or serum sample for β-hCG testing. Ensure that the test is negative before vaccinating.

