- 7. For females, ensure agreement and compliance with pregnancy prevention before vaccinating.
- 8. Confirm that all criteria for vaccination have been met according to inclusion/exclusion criteria
- 9. Confirm continued eligibility to receive vaccination
- 10. Obtain approximately 46.5 mL of blood for CBC with differential and platelet count, ALT, creatinine, malaria blood smear and PCR, anti-Pfs230 antibody ELISA, cellular and ex vivo assays, SMFA, and transcriptional analysis.
- 11. Administer the vaccine.

The following evaluations/procedures will be completed following vaccination:

- 1. Observe the subject for at least 30 minutes after vaccination to evaluate immediate adverse reactions.
- 2. Record vital signs (blood pressure, temperature, and heart rate).
- 3. Perform interim history and physical examination, focusing on any acute complaints.
- 4. Record AEs and concomitant medications, if applicable.

Study Day 2 (±0 days; 1 day after Vaccination #1)

- 1. Perform basic history and focused physical examination (including injection site), emphasizing examination of any acute complaints.
- 2. Record vital signs (blood pressure, temperature, and heart rate).
- 3. Record AEs and concomitant medications, if applicable.

Study Day 4 (±1 day; 3 days after Vaccination #1)

- 1. Perform basic history and focused physical examination (including injection site), emphasizing examination of any acute complaints.
- 2. Record vital signs (blood pressure, temperature, and heart rate).
- 3. Record AEs and concomitant medications, if applicable.
- 4. Obtain approximately 6.0 mL of blood for CBC with differential and platelet count, ALT, creatinine, and transcriptional analysis.

Study Day 8 (±2 days; 7 days after Vaccination #1)

- 1. Perform basic history and focused physical examination (including injection site), emphasizing examination of any acute complaints.
- 2. Record vital signs (blood pressure, temperature, and heart rate).
- 3. Record AEs and concomitant medications, if applicable.

Study Day 15 (±3 days; 14 days after Vaccination #1)

- 1. Perform basic history and focused physical examination, emphasizing examination of any acute complaints.
- 2. Record vital signs (blood pressure, temperature, and heart rate).
- 3. Record AEs and concomitant medications, if applicable.

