- 4. Obtain approximately 37 mL of blood for CBC with differential and platelet count, ALT, creatinine, malaria blood smear, anti-Pfs230 antibody ELISA, cellular and ex vivo assays, SMFA and transcriptional analysis.

Study Day 29 (±7 days; day of Vaccination #2)

The following evaluations/procedures will be completed before vaccination:

- 1. Perform interim history and physical examination, focusing on any acute complaints.
- 2. Record vital signs (blood pressure, temperature, and heart rate).
- 3. During the physical examination, study staff will educate the subject regarding signs and symptoms of potential adverse events (AEs) and indications for use of antipyretics if fever, headache, or malaise occurs.
- 4. For females, obtain a urine or serum sample for β-hCG testing. Ensure that the test is negative before vaccinating.
- 5. For females, ensure agreement and compliance with pregnancy prevention before vaccinating
- 6. Obtain approximately 16.5 mL of blood for CBC with differential and platelet count, ALT, creatinine, malaria blood smear, anti-Pfs230 antibody ELISA, SMFA and transcriptional analysis.
- 7. Confirm continued eligibility to receive vaccination.
- 8. Administer the vaccine.

The following evaluations/procedures will be completed following vaccination:

- 1. Observe the subject for at least 30 minutes after vaccination to evaluate immediate adverse reactions.
- 2. Record vital signs (blood pressure, temperature, and heart rate).
- 3. Perform interim history and physical examination, focusing on any acute complaints.
- 4. Record AEs and concomitant medications, if applicable.

Study Day 30 (±0 days; 1 day after Vaccination #2)

- 1. Perform basic history and focused physical examination (including injection site), emphasizing examination of any acute complaints.
- 2. Record vital signs (blood pressure, temperature, and heart rate).
- 3. Record AEs and concomitant medications, if applicable.

Study Day 32 (±1 day; 3 days after Vaccination #2)

- 1. Perform basic history and focused physical examination (including injection site), emphasizing examination of any acute complaints.
- 2. Record vital signs (blood pressure, temperature, and heart rate).
- 3. Record AEs and concomitant medications, if applicable.
- 4. Obtain approximately 6.0 mL of blood for CBC with differential and platelet count, ALT, creatinine, and transcriptional analysis.

Study Day 36 (±2 days; 7 days after Vaccination #2)

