- 4. Obtain approximately 6 mL of blood for CBC with differential and platelet count, ALT, creatinine, malaria smear, and transcriptional analysis.

Study Day 64 (±2 day; 7 days after Vaccination #3)

- 1. Perform basic history and focused physical examination (including injection site), emphasizing examination of any acute complaints.
- 2. Record vital signs (blood pressure, temperature, and heart rate).
- 3. Record AEs and concomitant medications, if applicable.

Study Day 71 (±3 days; 14 days after Vaccination #3)

- 1. Perform basic history and focused physical examination (including injection site), emphasizing examination of any acute complaints.
- 2. Record vital signs (blood pressure, temperature, and heart rate).
- 3. Record AEs and concomitant medications, if applicable.
- 4. Obtain approximately 16.5 mL of blood for CBC with differential and platelet count, ALT, creatinine, malaria blood smear, anti-Pfs230 antibody ELISA, SMFA and transcriptional analysis.

Study Day 85 (±14 days; 28 days after Vaccination #3)

- 1. Perform basic history and focused physical examination, emphasizing examination of any acute complaints.
- 2. Record vital signs (blood pressure, temperature, and heart rate).
- 3. Record AEs and concomitant medications, if applicable
- 4. Obtain approximately 5.5 mL of blood for CBC with differential and platelet count, ALT, creatinine, and blood smear.

Study Day 113 (±14 days; 56 days after Vaccination #3)

- 1. Perform basic history and focused physical examination, emphasizing examination of any acute complaints.
- 2. Record vital signs (blood pressure, temperature, and heart rate).
- 3. Record AEs and concomitant medications, if applicable.
- 4. Obtain approximately 30.5 mL of blood for malaria blood smear and for cellular and ex-vivo assays.

Study Day 141 (±28 days; 84 days after Vaccination #3)

- 1. Perform basic history and focused physical examination, emphasizing examination of any acute complaints.
- 2. Record vital signs (blood pressure, temperature, and heart rate).
- 3. Record AEs and concomitant medications, if applicable.
- 4. For females, obtain a urine or serum sample for β-hCG testing. Ensure that the test is negative before proceeding.
- 5. Obtain approximately 11.5 mL of blood for malaria blood smear, anti-Pfs230 antibody ELISA, standard membrane feeding assay (SMFA) and transcriptional analysis.

Study Day 225 (±28 days; 168 days after Vaccination #3)

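### The visit that closes the 7-day adverse event period may be held on day 5, leaving events on days 6-7 to self-report or later recall

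*Combined protocol and SAP*

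**What the plan says.** Appendix A places a visit 7 days after each dose, with the same tolerance each time: "Study Day 8 (±2 days; 7 days after Vaccination #1", "Study Day 36 (±2 days; 7 days after Vaccination #2" and "Study Day 64 (±2 day; 7 days after Vaccination #3". The footnote to the schedule fixes the anchor: "Visit windows are based off timing of days post the preceding vaccination".

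For dose 1, the contact before this visit is "Study Day 4 (±1 day; 3 days after Vaccination #1" and the contact after it is "Study Day 15 (±3 days; 14 days after Vaccination #1". Doses 2 and 3 follow the same pattern. At the visit 14 days after the dose, the day-to-day schedule names the injection site as part of the examination after dose 3 (Day 71), but not after doses 1 and 2 (Days 15 and 43).

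Section 12.3 sets the recording period. Solicited and "unsolicited AEs will be recorded through 7 days after each vaccination", or until resolved. After that, recording is limited to unsolicited events, serious events, unanticipated problems and new chronic illness. Section 12.2 has events elicited at every contact and a clinician available throughout. No diary, telephone call or home visit is described between the Day 7 and Day 14 visits.

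Two provisions use the same 7 days. Section 14.2 compares doses by a Wilcoxon signed-rank test on "the difference between the numbers of AEs in the 7 days following each vaccination". Section 12.9 counts related Grade 3 events lasting 48 hours or more within 7 days of vaccination toward a study halt.

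**The concern.** A period that is defined as 7 days should end with a look-back that reaches day 7. Here a fully compliant site can hold the closing visit on day 5, and the plan schedules nothing else until day 11 at the earliest. A mild headache or sore arm that begins on day 6 may have resolved by then, and after doses 1 and 2 the later visit does not list an injection-site examination.

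Three things are at stake:

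- **Solicited reactogenicity.** Its completeness for the last two days of the period depends on recall or self-report.
- **The dose-to-dose comparison.** It treats each count as covering 7 days, while the part covered by a scheduled in-period look-back can differ between doses in the same person.
- **Timeliness of safety information.** A Grade 3 clinical event on day 6 or 7 may first be elicited at a scheduled visit after the next pilot dose level has begun.

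**Working it through.** **Inputs.** Visit windows and their anchor: Appendix A. Recording period: Section 12.3. Pilot staging: Section 1.2.1 and Table 1. Halting counts: Section 12.9. Safety detection figures: Section 14.1.

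**1. The plan's own figures.** Section 14.1 gives the chance of seeing at least one serious or severe event, which is 1 − (1 − p)^n.

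| n | p | Stated | Recomputed |
|---|---|---|---|
| 20 | 0.077 | 0.80 | 0.799 |
| 20 | 0.109 | 0.90 | 0.901 |
| 60 | 0.026 | 0.80 | 0.794 |
| 60 | 0.037 | 0.90 | 0.896 |

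They reproduce. None of them depends on the visit window, and the plan states no figure that does.

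**2. Windows in post-vaccination days.**

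- Day 3 visit: 3 ± 1 = 2 to 4
- Day 7 visit: 7 ± 2 = 5 to 9
- Day 14 visit: 14 ± 3 = 11 to 17

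**3. Days without a scheduled in-period look-back.** With the closing visit on day 5, these are days 6 and 7: 2/7 = 29% of the period. The gap to the next visit is 11 − 5 = 6 to 17 − 5 = 12 days. For an event on day 6 or 7, recall spans from 11 − 7 = 4 to 17 − 6 = 11 days.

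**4. Dose-to-dose comparison.** The scheduled in-period look-back ends on the earlier of the visit day and day 7, so it covers 5 to 7 days. Within one person it can differ between two doses by up to 7 − 5 = 2 days.

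**5. Pilot staging.** In the Table 1 example, the first dose level starts on Study Day 1 and the second on Study Day 15. Post-vaccination day d is Study Day d + 1. After an early closing visit, an event on days 6-7 may first be elicited at a scheduled visit on Study Day 12 to 18, which can be up to 18 − 15 = 3 days after the second dose level starts. A closing visit with a 0 to +2 window would fall on Study Day 8 to 10, at least 15 − 10 = 5 days before it.

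**6. Halting rule, illustration only.** Let p be the true probability per participant of a qualifying Grade 3 event and f the share of such events never captured. The chance of meeting the rule is P(X ≥ r) with X ~ Binomial(n, p(1 − f)). Both p = 0.20 and the values of f are assumptions.

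| f | Main Group, 4 or more of 20 | Pilot Group, 2 or more of 5 |
|---|---|---|
| 0 | 0.589 | 0.263 |
| 5% | 0.544 | 0.242 |
| 10% | 0.497 | 0.222 |
| 20% | 0.401 | 0.183 |

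Here f is the product of three shares: visits held early, qualifying events starting after such a visit but within day 7, and those events never reported later. The documents give none of the three. The table shows sensitivity; it is not an estimate of loss.

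**The case against.** The strongest reply is that the 7 days say when an event must occur, not when it must be elicited. Adverse events are assessed at every visit, including Day 14. A clinician is available at all times (Section 12.2), and participants are asked to report any medical issue up to 12 months after the final dose (Section 12.5.5). A reader might infer that days 6-7 go unobserved. The documents do not support that: what is missing is a scheduled in-period contact, and capture becomes late or dependent on recall. This part of the reply stands.

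A reader might also infer that a day-6 event labelled unsolicited drops out of the signed-rank test or the halting rule. It does not. Section 14.2 counts adverse events without that distinction, and Section 12.9 counts Grade 3 events of either kind. Mislabelling affects only the solicited/other split in the tables.

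The halting rule is also less exposed than it may seem. Its serious-event and hypersensitivity criteria carry no 7-day limit, and no laboratory samples are drawn at the Day 7 visit. A Grade 3 event lasting 48 hours or more is unlikely to be forgotten by Day 14, although the documents give no data on this.

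Three things survive the reply. Section 12.3 does not say how an event with onset on day 6, first mentioned on day 14, is to be classified. The Day 14 visit is a weaker backstop for local reactions after doses 1 and 2 than after dose 3. And elicitation at Day 14 may be too late to inform the next pilot step.

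**Conclusion.** The gap is real and minor. In participants seen early, up to 2 of 7 days (29%) after a dose have no scheduled in-period look-back, and events on those days rest on self-report or on recall over 4 to 11 days. The consequences are less complete solicited data, added noise in the dose-to-dose test, and possible delay in learning of a Grade 3 clinical event.

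Two wider conclusions might be drawn, and neither holds. The primary endpoint as a whole is not cut short, because Section 5.1 defines it as the incidence of local and systemic adverse events and serious adverse events without a 7-day limit; only its solicited component is bounded that way. Nor is a between-arm bias shown, because every arm has the same windows under blinding.

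The 29% is a share of calendar days in the worst permitted case, not a share of events. The documents give neither onset times nor the frequency of early visits, so the loss cannot be estimated. That it is small is a judgement, resting on the assumption that most reactions begin before day 6.

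**What to change.** Set the window for the Study Day 8, 36 and 64 visits at 0 to +2 days, so that the closing look-back reaches day 7 after every dose. In Section 12.3, state that events of the listed types with onset on days 0-7 are tabulated as solicited whenever they are elicited. The second change settles the classification, including events that begin on day 7 after the visit has taken place. The first replaces long recall and, in the pilot, puts the look-back before the next dose level in the Table 1 example.

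The cost is two fewer permitted early days at three visits, hence less scheduling flexibility. No visit, blood draw or participant is added, and no dose or halting criterion changes.

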6.4 Exclusion Criteria

An individual will be excluded from participating in this trial if any one of the following criteria is fulfilled:

- 1. Pregnant, as determined by a positive urine or serum beta human choriogonadotropin (β-hCG) test (*if female*).
 - NOTE: Pregnancy is also a criterion for discontinuation of any further vaccine dosing.
- 2. Behavioral, cognitive, or psychiatric disease that in the opinion of the investigator affects the ability of the subject to understand and comply with the study protocol at a level appropriate for the subject's age.
- 3. Hemoglobin, white blood cell (WBC), absolute neutrophil count, or platelet levels outside the local laboratory-defined limits of normal. (Subjects may be included at the investigator's discretion for "not clinically significant" values outside of normal range and ≤ Grade 2.)
- 4. Alanine transaminase (ALT) or creatinine (Cr) level above the local laboratory-defined upper limit of normal. (Subjects may be included at the investigator's discretion for "not clinically significant" values outside of normal range and ≤ Grade 2.)
- 5. Infected with HIV.
- 6. Evidence of clinically significant neurologic, cardiac, pulmonary, hepatic, endocrine, rheumatologic, autoimmune, hematological, oncologic, or renal disease by history, physical examination, and/or laboratory studies.
- 7. History of receiving any investigational product within the past 30 days.
- 8. Current or planned participation in an investigational vaccine study until the time period of the last required study visit under this protocol.
- 9. Medical, occupational, or family problems as a result of alcohol or illicit drug use during the past 12 months.
- 10. History of a severe allergic reaction or anaphylaxis.

11. Known:

- Severe asthma, defined as asthma that is unstable or required emergent care, urgent care, hospitalization, or intubation during the past 2 years, or that has required the use of oral or parenteral corticosteroids at any time during the past 2 years.
- Autoimmune or antibody-mediated disease including but not limited to: systemic lupus erythematosus, rheumatoid arthritis, multiple sclerosis, Sjögren's syndrome, or autoimmune thrombocytopenia.
- Immunodeficiency syndrome.
- Seizure disorder (exception: history of simple febrile seizures).
- Asplenia or functional asplenia.

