7.4 Contraindications to Vaccination

The following criteria should be checked prior to each study vaccination and are contraindications to further vaccination with either the experimental vaccine or the rabies vaccine:

- Hypersensitivity reaction following administration of the study vaccine or comparator.
- Positive urine or serum β-hCG test prior to vaccination.

Subjects who receive at least 1 dose of study vaccine under this protocol prior to developing a contraindication will be encouraged to remain in the study for safety evaluation of the dose(s) already received and complete research visits for immunogenicity and functional activity if deemed safe by the PI. Subjects who have a positive β -hCG test prior to their first study vaccination may be withdrawn from the study and replaced.

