15.4.1.2 General Study Vaccine Risks

The study vaccine can cause non-specific inflammation and may be harmful while pregnant (Section 6.5). Therefore, pregnant women are excluded from study participation, and women of reproductive potential will be required to agree to use birth control as outlined in Section 6.3 and will be tested for pregnancy prior to each study vaccine administration.

As with any vaccine, immediate hypersensitivity reactions including urticaria, anaphylaxis, or other IgE-mediated responses are possible. There is a theoretical possibility of risks about which we have no present knowledge. Subjects will be informed of any such risks should further data become available.

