Appendix A. Schedule of Assessments and Day-to-Day Schedule

		Months			0					1					2					3	4	5	8	10	12	14
Arms: 1a, 1b, 1c, 1d, 2a, 2b, 2	c, 2d	Visits		1	2	3	4	5	6	7	8	9	10	11	12	13	14	15	16	17	18	19	20	21	22	23
		Study Day (4)		-7	1	,	4	2	15	29	30	32	36	43	57	58	60	64	71	85	113	141	225	281	337	393
		Study Day (4)	Screening	-/	1	-		0	13	27	30	32	30	40	31	30	00	U-7	/1	0.5	113	107	223	201	331	373
Procedures	Collection	Days Post Vac	Screening	-7	0	1	3	7	14	0	1	3	7	14	0	1	3	7	14	28	56	84	168	224	280	336
Trocedures	Tube	Visit																								
		Windows		+/-7	0	0	±1	±2	±3	±7	0	±1	±2	±3	±7	±0	±1	±2	±3	±14	±14	±28	±28	±28	±28	±28
Clinical Procedures		(days) (1)																								
Complete medical history physical																										
(2)			X																							
Informed consent			X																							
Pre-test/Post-test HIV counseling			X																							
Interim clinical evaluation				X	X	X	X	X	X	X	X	X	X	X	X	X	X	X	X	X	X	X	X	X	X	X
AE/SAE assessment				X	X	X	X	X	X	X	X	X	X	X	X	X	X	X	X	X	X	X	X	X	X	X
Pregnancy prevention			X	X	X	X	X	X	X	X	X	X	X	X	X	X	X	X	X	X						
Conmed review			X	X	X	X	X	X	X	X	X	X	X	X	X	X	X	X	X	X	X	X	X	X	X	X
VACCINATION					X					X					X											
Unblinding																										X
Laboratory Procedures						_		_			_					_		_					_			_
CBC with differential	EDTA		2	2	2		2		2	2		2		2	2		2		2	2						
ALT/Creatinine	SST		3	3	3		3		3	3		3		3	3		3		3	3						
Hepatitis B, C, HIV testing	SST		5																							
Urine/Serum pregnancy test	Urine Container or		x	x	x					x					x											
(females only)	SST		Λ	Λ	Λ					Λ.					Λ											
TBS (# indicates collect for PCR as well)	TBD			0.5#	0.5#				0.5	0.5				0.5	0.5				0.5	0.5	0.5	0.5	0.5		0.5	0.5
Pfs230 ELISA	SST			20	10				10	10				10	10				10			10	20		10	10
SMFA	331			20	10				10	10				10	10				10			10	20		10	10
Cellular assays/B cell studies	NaHep			30	30				20					20							30					
Ex vivo assays	Манер				X				X					X							X					
Transcriptional analysis	PAXGene			1	1	0	1		1	1		1		1	1		1		1			1	1			
Daily blood draw vol	ume in mL (3)		10	56	46	0	6	0	37	16.5	0	6	0	36.5	16.5	0	6	0	16.5	5.5	30.5	11.5	21.5	0	10.5	10.5
Cumulative blood vo	olume in mL		10	66	112	112.0	118	118	155	171	171	177	177	214	230	230	236	236	253	258	289	300	321.5	322	332	342.5
Compensati	ion		6	6	6	3	6	6	6	6	3	6	6	6	6	3	6	6	6	6	6	6	6	6	6	6

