- 1. Perform basic history and focused physical examination (including injection site), emphasizing examination of any acute complaints.
- 2. Record vital signs (blood pressure, temperature, and heart rate).
- 3. Record AEs and concomitant medications, if applicable.

Study Day 43 (±3 days; 14 days after Vaccination #2)

- 1. Perform basic history and focused physical examination, emphasizing examination of any acute complaints.
- 2. Record vital signs (blood pressure, temperature, and heart rate).
- 3. Record AEs and concomitant medications, if applicable.
- 4. Obtain approximately 36.5 mL of blood for CBC with differential and platelet count, ALT, creatinine, malaria blood smear, anti-Pfs230 antibody ELISA, cellular and ex vivo assays, SMFA and transcriptional analysis.

Study Day 57 (±7 days; day of Vaccination #3)

- 1. Perform basic history and focused physical examination, emphasizing examination of any acute complaints.
- 2. Record vital signs (blood pressure, temperature, and heart rate).
- 3. Record AEs and concomitant medications, if applicable.
- 4. For females, ensure agreement and compliance with pregnancy prevention before vaccination

The following evaluations/procedures will be completed following vaccination:

- 1. Observe the subject for at least 30 minutes after vaccination to evaluate immediate adverse reactions.
- 2. Record vital signs (blood pressure, temperature, and heart rate).
- 3. Perform interim history and physical examination, focusing on any acute complaints.
- 4. Record AEs and concomitant medications, if applicable
- 5. Obtain approximately 16.5 mL of blood for CBC with differential and platelet count, ALT, creatinine, malaria blood smear, anti-Pfs230 anti body ELISA and transcriptional analysis.

Study Day 58 (±0 days; 1 day after Vaccination #3)

- 1. Perform basic history and focused physical examination (including injection site), emphasizing examination of any acute complaints.
- 2. Record vital signs (blood pressure, temperature, and heart rate).
- 3. Record AEs and concomitant medications, if applicable.

Study Day 60 (±1 day; 3 days after Vaccination #3)

- 1. Perform basic history and focused physical examination (including injection site), emphasizing examination of any acute complaints.
- 2. Record vital signs (blood pressure, temperature, and heart rate).
- 3. Record AEs and concomitant medications, if applicable.

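### The Day 57 visit list omits the pregnancy test and eligibility check before dose 3 and places the blood draw after the injection, unlike Days 1 and 29

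*Combined protocol and SAP*

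**What the plan says.** The protocol requires a pregnancy check before every dose in several places:

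- Section 6.4, criterion 1: "Pregnancy is also a criterion for discontinuation of any further vaccine dosing".
- Section 7.4: "The following criteria should be checked prior to each study vaccination". A positive β-hCG result is one of the two criteria.
- Section 15.4.1.2: women of reproductive potential "will be tested for pregnancy prior to each study vaccine administration".
- Appendix A, schedule table: the row "Urine/Serum pregnancy test" is marked at Screening and at Days -7, 1, 29 and 57, so it covers all three vaccination days.

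The Day 1 and Day 29 lists in the day-to-day schedule follow this. Each instructs staff, before dosing: "For females, obtain a urine or serum sample for β-hCG testing. Ensure that the test is negative before vaccinating". Each also has the step "Confirm continued eligibility to receive vaccination" and takes the blood sample before the line to give the vaccine.

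The Day 57 list differs. It has four steps ahead of its post-vaccination heading: history and examination, vital signs, adverse events and medications, and "For females, ensure agreement and compliance with pregnancy prevention before vaccination". The blood draw is the fifth step under the post-vaccination heading. It covers blood count, ALT, creatinine, and "malaria blood smear, anti-Pfs230 anti body ELISA and transcriptional analysis".

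**The concern.** The product is first-in-human, and Section 6.5.1 states that its effects on the fetus are unknown. Under Section 12.5.4, pregnancy in a participant possibly exposed to study agent leads to unblinding and to stopping the study agent. The test is what detects a pregnancy before the last dose; asking about contraception does not replace it. Two parts of the same appendix disagree, and nothing says which prevails.

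The draw order matters for different reasons. Read literally, dose 3 would have no same-day pre-dose safety laboratories. An abnormality already present before the injection could first appear in a sample taken after it, and so fall in the 7-day post-vaccination window that the pausing and halting rules use (Sections 12.8.1 and 12.9). The exploratory RNA-sequencing objective contrasts the immune state ahead of vaccination with the state soon after, and Section 9.6.3 refers to transcript changes following each dose. A sample taken after the injection on Day 57 is not a clean baseline for dose 3.

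**Working it through.** The plan states no figure on this point, so the check compares the three dosing-day lists and then works out the intervals.

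**Lists side by side (Appendix A, day-to-day schedule)**

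| Step | Day 1 | Day 29 | Day 57 |
|---|---|---|---|
| β-hCG test negative before dosing | pre-dose, item 6 | pre-dose, item 4 | absent |
| Contraception check | pre-dose, item 7 | pre-dose, item 5 | pre-dose, item 4 |
| Eligibility confirmed | pre-dose, item 9 | pre-dose, item 7 | absent |
| Blood draw | pre-dose, item 10 | pre-dose, item 6 | post-dose, item 5 |
| Line to give the vaccine | item 11 | item 8 | absent |

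The Day 57 numbering runs 1 to 4 and then 1 to 5 without a break, so the missing steps do not look like text lost in conversion.

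**Pregnancy tests scheduled**

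- Table: Screening, Days -7, 1, 29, 57.
- Visit lists, from Day -7 onward: Days -7, 1, 29, 141.

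The lists drop Day 57 and add Day 141, when no vaccine is given. This may be a misplaced item.

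**Intervals.** Footnote 1 of the table counts visit windows from the preceding vaccination.

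- Dose 3 (Day 57) falls 28 ± 7 days after dose 2, so 21 to 35 days. The Day 29 test is done at dose 2, so on the list alone the last test precedes dose 3 by 28 days (21 to 35).
- Day 43 falls 14 ± 3 days after dose 2, so 11 to 17 days. The gap from the Day 43 draw to dose 3 is 28 − 14 = 14 days; minimum 21 − 17 = 4, maximum 35 − 11 = 24.
- Day 141 falls 84 ± 28 days after dose 3, so 56 to 112 days. The gap between listed tests, Day 29 to Day 141, is 28 + 84 = 112 days; minimum 21 + 56 = 77, maximum 35 + 112 = 147.

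**Blood volume at Day 57, from the table**

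2 (blood count) + 3 (ALT and creatinine) + 0.5 (smear) + 10 (shared ELISA/SMFA serum) + 1 (PAXGene) = 16.5 mL.

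This equals the volume in the list. The serum for SMFA is therefore collected although the Day 57 text does not name SMFA. The lists and the table differ in content, and the lists differ in order, but the volume agrees.

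**The case against.** The strongest reply is that the test is already required by the table, Section 7.4 and Section 15.4.1.2. The Day 57 list is silent and does not waive it: doing the test satisfies every part of the protocol, and skipping it breaches three. Eligibility is likewise covered by the contraindications in Section 7.4 and the deferral criteria in Section 7.5, which apply at each scheduled vaccination. Women of childbearing potential must also use an injectable, implantable or intrauterine method (Section 6.3), and the Day 57 list does check compliance. The 28-day gap arises only if staff follow the list and nothing else. The interval to Day 141 cannot affect dose 3, because no vaccine is given after it. No section sets a draw order, no dosing decision is tied to same-day laboratory results, and the RNA objective is exploratory.

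Much of this stands, and it limits the size of the problem. This is an internal inconsistency, the eligibility omission has little consequence of its own, and the Day 141 interval is peripheral. It does not remove the need for correction. The visit list is the step-by-step instruction for the day, and it leaves out a safeguard that the rest of the protocol requires. The draw order is not corrected anywhere else in the protocol, so staff following the text would sample after the injection.

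**Conclusion.** The concern holds and should be corrected. At one of the three dosing visits, the list omits the β-hCG test and the eligibility confirmation and puts the draw after the injection. The omitted test conflicts with the table and with Sections 7.4 and 15.4.1.2. The draw order conflicts only with the Day 1 and Day 29 lists.

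The intervals of 28 days since the last pregnancy test (21 to 35) and 14 days since the last draw (4 to 24) assume that staff follow the list alone. The test affects only women of childbearing potential, whose number the documents do not give. The draw order affects one of the three dosing-day safety-laboratory and transcriptome samples. The effect on ELISA is negligible, no laboratory gate on dosing is defeated, and power and alpha are unchanged.

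**What to change.** Replace the Day 57 list with the Day 29 sequence:

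1. History, examination, vital signs and participant education.
2. β-hCG test, negative before dosing.
3. Contraception check.
4. The 16.5 mL draw, naming SMFA and labelled as the pre-dose 3 sample.
5. Eligibility confirmation.
6. Vaccine administration.
7. Post-dose observation, vital signs, interim history and examination, and adverse event recording.

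Either delete the Day 141 β-hCG test or add it to the table. Deletion looks simpler, since that visit is at least 56 days after dose 3 and the contraception requirement ends 1 month after it.

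The cost is wording in Appendix A, submitted as an amendment under Section 16.3. The table already carries the Day 57 pregnancy test and the 16.5 mL draw, so the new Day 57 list adds no visit, test or blood volume to it.
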